9.3.3.1 Study Safety Evaluation Criteria

If any of the following events occur in a subject in the study who has received BMN 270 infusion, an urgent evaluation by the DMC will be required and further enrollment into the trial will be temporarily put on hold if recommended by the DMC per Section 9.1.

1. Liver dysfunction (criteria do not apply to ALT elevations with an extra-hepatic etiology):
 - ALT > 5x ULN, for more than 2 weeks
 - ALT > 3x ULN **and** (total bilirubin > 2x ULN **or** INR >1.5)
 - ALT > 3x ULN with signs and symptoms of liver dysfunction
2. The occurrence of Grade 4 or Grade 5 adverse events assessed as related to study drug (events of liver dysfunction are defined above).
3. The occurrence of an AE of hepatic failure.
4. The detection of high-titer neutralizing antibodies (>5 BU) to hFVIII following BMN 270 infusion in two subjects.
5. The occurrence of any cancer (except non-melanoma skin cancer) at any point after BMN 270 infusion.
6. The occurrence of a thromboembolic event with FVIII activity > 150 IU/dL in one subject.

If any of the following events occurs in a subject in the study who has received BMN 270 infusion, an urgent evaluation by the DMC will be required. Further enrollment into the trial will continue while DMC evaluation is ongoing, unless deemed otherwise by the DMC:

1. The detection of high-titer neutralizing antibodies (>5 BU) to hFVIII following BMN 270 infusion in one subject.
2. Occurrence of a thromboembolic event in one subject.

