10.2.1 Events of Special Interest (EOSI)

The following EOSI need to be reported to the Sponsor within 24 hours of site awareness, irrespective of seriousness, severity or causality:

- Elevation of ALT > ULN or > 1.5x baseline value, regardless of whether that elevation triggers an initiation or modification of oral corticosteroid treatment
- Thromboembolic event
- Immediate reactions: infusion-related reactions, hypersensitivity adverse events, or anaphylaxis
- Development of anti-FVIII inhibitory antibodies (inhibitors)

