Date of Original Protocol:	28 February 2020
Date of Amendment 1:	15 September 2020

Property of BioMarin

CONFIDENTIAL

May not be divulged, published, or otherwise disclosed to others without prior written approval from BioMarin.

This study will be conducted according to the principles of Good Clinical Practice as described in the U.S. Code of Federal Regulations and the International Conference on Harmonisation Guidelines, including the archiving of essential documents

CLINICAL STUDY PROTOCOL AMENDMENT SUMMARY**Amendment 1****Date: 15 September 2020****RATIONALE AND SUMMARY OF CHANGES**

A summary of major changes covered by Amendment 1 to the 270-303 protocol is provided below:

1. Screening testing for COVID-19 has been added.

Rationale: Exclusion criteria for the study already included a provision excluding subjects with an active infection. In light of the emergence of the novel coronavirus SARS-CoV-2, the criterion has been modified to specify that this includes testing for active COVID-19 infection, which has been added to the Screening visit in the Schedule of Activities.

2. The occurrence of events of Hy's law has been added as an event of special interest (EOSI) for purposes of expedited safety reporting, and additional safety monitoring in the event of a case potentially meeting Hy's law criteria has been added.

Rationale: Events potentially meeting the criteria for Hy's law involve combined assessment of elevations in aminotransferases and total bilirubin levels, while the current list of EOSI focuses on elevations in aminotransferases. To date, no events meeting the criteria for Hy's law have been reported in any BMN 270 study. While monitoring for events of Hy's law has been ongoing as part of routine pharmacovigilance in all BMN 270 studies, this change ensures that the occurrence of any events in the future will be reported in an expedited manner. In addition, expanded laboratory monitoring (to include albumin and PT/INR) has been added to the guidelines for evaluating potential Hy's law cases.

3. Language has been added concerning the use of liver biopsy sample information for biopsies performed for safety-related reasons.

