7.4 Summary of Overall Risks and Benefits

Overall, 151 subjects have received a BMN 270 infusion at one of 4 dose levels (6E12 vg/kg, 2E13 vg/kg, 4E13 vg/kg, or 6E13 vg/kg) in one of the four ongoing BMN 270 clinical studies (270-201, 270-301, 270-302, 270-203). Single infusions have been generally well tolerated by treated subjects across all investigated doses. All subjects have successfully completed their full-dose infusion of BMN 270, with no infusions requiring permanent termination prior to completion due to AEs. No deaths have been reported in any of the

BMN 270 studies, and no participants discontinued from studies as a result of an AE. Frequency of adverse events decreased over time with no delayed adverse drug reactions.

Transient, asymptomatic ALT elevation (grade 1 to 3 in severity) has been observed in most subjects administered BMN 270 shortly after dosing, with no symptoms or sequelae suggestive of clinically significant hepatocyte injury or liver dysfunction; no events meeting the Hy's Law criteria have been identified. ALT elevations have been reported as events of interest in 13 subjects in 270-201, 1 subject in 270-302, and 91 subjects in 270-301.

Although the majority of events have been Grade 1 or Grade 2 in severity, 11 subjects (1 in 270-302 and 10 in 270-301) had a reported Grade 3 ALT elevation. Only one serious event of ALT increased has been reported by investigators (in addition to one event that BioMarin conservatively assessed as serious based on the details of the case). While the majority of ALT elevations responded rapidly to corticosteroids, given current interest in the field of AAV gene therapy for the use of non-steroidal approaches to managing or preventing ALT elevations, alternate non-steroidal systemic immunosuppressive agents have also been used to manage hepatic reactions where corticosteroids have proven to be ineffective or where high doses/and or prolonged exposure to corticosteroids have led to unwanted side effects. Overall, the literature and clinical experience with BMN 270 suggests that transient elevations in liver enzymes are expected following AAV-based gene therapy for the treatment for hemophilia A or B without any long-term concerns of hepatic injury ([Manno, 2006](#); [Nathwani, 2011](#); [George, 2016](#); [Miesbach, 2016](#); [Pasi, 2017](#)).

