10.2.1 Events of Special Interest (EOSI)

The following EOSI need to be reported to the Sponsor within 24 hours of site awareness, irrespective of seriousness, severity or causality:

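### The combined liver criterion for mandatory urgent DMC evaluation (Amendment 1, section 9.3.3.1) names ALT only, so an AST-led case with raised bilirubin meets no laboratory trigger

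*Protocol*

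**What the plan says.** Section 9.3.3.1 of Amendment 1 names the events after which the DMC must carry out an urgent evaluation, with enrollment held if the DMC so recommends. The first item is liver dysfunction, with three alternative criteria:

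- ALT above 5x ULN lasting longer than two weeks;
- the combined criterion, "ALT > 3x ULN and (total bilirubin > 2x ULN or INR >1.5";
- ALT above 3x ULN with clinical signs and symptoms.

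The lead-in carries an exception: "criteria do not apply to ALT elevations with an extra-hepatic etiology". The second item covers Grade 4 or 5 events related to study drug, with the remark that "events of liver dysfunction are defined above". The third is an adverse event of hepatic failure. The original protocol has the same list.

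Elsewhere, item 2 of the Amendment 1 summary of changes says that potential Hy's-law events "involve combined assessment of elevations in aminotransferases and total bilirubin levels", and makes Hy's-law events an event of special interest (EOSI). Section 10.2.1 states: "The following EOSI need to be reported to the Sponsor within 24 hours of site awareness". In section 9.7.8.3, the line on combined elevation in Table 9.7.8.3.2 is worded for ALT or AST at or above 3x ULN with total bilirubin at or above 2x ULN. It stands inside the row for ALT at or above 3x ULN. Table 9.7.8.3.1 puts AST and total bilirubin in every liver panel.

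**The concern.** The list in section 9.3.3.1 is where the protocol replaces discretion with an obligation to bring in the independent committee. A raised aminotransferase together with raised bilirubin is the pattern that Amendment 1 set out to capture more firmly. Its own description of that pattern is not limited to ALT, but the DMC list is.

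A subject whose AST has crossed 3x ULN with bilirubin above 2x ULN, while ALT sits just under 3x ULN, would thus not oblige anyone to convene the DMC. At stake is whether an independent body looks promptly at such a case while other subjects are waiting for a single-dose vector that cannot be withdrawn once given.

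**Working it through.** The plan gives no figure on this point, so the check is a reading of the rules followed by a bound on frequency.

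**1. Logic of the list.** Each of the three liver criteria needs ALT above 3x ULN (the 5x criterion implies it). If ALT is at or below 3x ULN, none can be met, whatever the AST, bilirubin, INR, duration or symptoms.

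**2. Illustration.** Take a subject without symptoms, with AST 3.5x ULN, total bilirubin 2.5x ULN and INR 1.6.

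| Liver criterion | Current text, ALT 2.9x | Current text, ALT 3.1x | AST added to the combined criterion, ALT 2.9x |
|---|---|---|---|
| ALT > 5x, over 2 weeks | no | no | no |
| Combined with bilirubin or INR | no (ALT 2.9x) | yes | yes (AST 3.5x) |
| ALT > 3x with symptoms | no | no | no |
| Met | 0 of 3 | 1 of 3 | 1 of 3 |

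The result does not depend on the INR, because bilirubin at 2.5x already satisfies that half of the criterion.

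**3. The other items on the list.** The Grade 4/5 item refers liver events back to the definitions above it, which are the ALT ones. The hepatic-failure item does apply, but it is a clinical judgement and probably a later stage. The remaining items (inhibitors, cancer, thromboembolism) do not concern liver laboratory values.

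**4. Frequency.** Inputs from section 7.4 of Amendment 1: "Overall, 151 subjects have received a BMN 270 infusion at one of 4 dose levels", and "no events meeting the Hy's Law criteria have been identified".

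- One-sided 95% upper limit for 0 of 151: 1 − 0.05^(1/151) = 0.0196, or 1.96%.
- Expected number among 20 subjects at that limit: 20 × 0.0196 = 0.39.
- With a two-sided 95% limit: 1 − 0.025^(1/151) = 0.0241, and 20 × 0.0241 = 0.48.

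These bound all Hy's-law cases, including those led by ALT, which the present list already catches. The AST-led subset can only be smaller, and no rate for it can be derived from the documents. The bound also assumes that the earlier studies are comparable, although their dose levels and steroid regimens differ.

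**The case against.** **ALT as the chosen marker.** ALT drives the steroid rules, the work-up table and the first EOSI of the original protocol, "Elevation of ALT > ULN or > 1.5x baseline value". AST also rises with muscle injury. An ALT-only trigger could be deliberate. What stands is that AST should not be added without widening the extra-hepatic exception. What does not stand is that AST is foreign to the protocol's view of the liver: exclusion criterion 3 already treats AST above 1.25x ULN as a sign of significant liver dysfunction.

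**Other safeguards.** By the amendment summary, Hy's-law events are EOSI and so go to the Sponsor within 24 hours. With ALT above ULN but below 3x ULN, Table 9.7.8.3.2 calls for repeat tests within 24-72 hours and consultation with the Medical Monitor, who must also approve each enrollment (section 9.4.5). The Sponsor may stop the study (section 9.3.3), and the DMC reviews data continuously and may pause enrollment (section 9.1). All of this stands. A reader might infer that such a case would go unseen, or that enrollment could not be halted; the documents do not support that. But the reporting and enrollment-approval routes are sponsor-side, and ongoing DMC review sets no urgent timing.

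**A contradiction?** A reader might also infer that the work-up table and the DMC list contradict each other. They do not, because the ALT-or-AST line sits in the row for ALT at or above 3x ULN.

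**Text not shown.** The amended EOSI list is cut off and the DMC Charter is not available. Either might send such a case to the DMC at once. This limits the point to the visible text.

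**INR.** The passages that pair aminotransferases with a second marker pair them with bilirubin. In the work-up table PT/INR is a follow-up test. Support for adding AST is therefore direct for the bilirubin limb only.

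**Conclusion.** The point holds as a narrow one. For AST above 3x ULN with total bilirubin above 2x ULN and ALT at or below 3x ULN, section 9.3.3.1 contains no laboratory trigger. What the visible text lacks is the automatic urgent convening of the independent committee, and nothing more.

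The practical effect is small. It would be wrong to read 0.39 as the number of cases likely to be missed: it is an upper confidence bound for every Hy's-law type, and it rests on comparability with the earlier studies. The conclusion also assumes that neither the unseen part of the amended EOSI list nor the DMC Charter forwards such cases urgently. Low priority: a cheap improvement to a stated safety rule, which could be made at the next amendment.

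**What to change.** In the second liver criterion of section 9.3.3.1, replace *ALT* with *ALT or AST* and leave the bilirubin and INR thresholds as they are. Widen the exception in the lead-in to cover *ALT or AST* elevations of extra-hepatic origin, so that muscle-related AST rises do not trigger a review.

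The bilirubin limb needs no new test, since AST and total bilirubin are in every liver panel. INR belongs to the coagulation screen, which is scheduled less often, so the INR limb would apply whenever an INR is available and need not add blood draws.

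Two items are optional tidying: use the same inequality signs as Table 9.7.8.3.2, and place that table's ALT-or-AST line so that it applies at any ALT level.

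The cost is a few words in one list and a rare extra DMC review.

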10.3.3.3 Causality

The Investigator will determine the relationship of an AE to the study drug and/or corticosteroids and/or other immunosuppressant agents and will record it on the source documents and AE eCRF. To ensure consistency of causality assessments, Investigators should apply the guidance in [Table 10.3.3.1](#).

Table 10.3.3.3.1: Causality Attribution Guidance

Relationship	Description
Not Related	
 • Exposure to the IP and/or corticosteroids has not occurred OR • The administration of the IP and/or corticosteroids and the occurrence of the AE are not reasonably related in time OR • The AE is considered likely to be related to an etiology other than the use of the IP and/or corticosteroids; that is, there are no facts, evidence, or arguments to suggest a causal relationship to the IP and/or corticosteroids.
Related	
 • The administration of the IP and/or corticosteroids and the occurrence of the AE are reasonably related in time AND • The AE could possibly be explained by factors or causes other than exposure to the IP and/or corticosteroids OR
	
 • The administration of IP and/or corticosteroids and the occurrence of the AE are reasonably related in time AND • The AE is more likely explained by exposure to the IP and/or corticosteroids than by other factors or causes.

Factors suggestive of a causal relationship could include (but are not limited to):

- Plausible temporal relationship
- Absence of alternative explanations
- Rarity of event in a given patient or disease state
- Absence of event prior to study drug and/or corticosteroid exposure
- Consistency with study product pharmacology
- Known relationship to underlying mechanism of study drug and/or corticosteroid action
- Similarity to adverse reactions seen with related drug products
- Abatement of AE with discontinuation of study drug and/or corticosteroids, and/or recurrence of AE with reintroduction of study drug and/or corticosteroids

The Investigator's assessment of causality for individual AE reports is part of the study documentation process. Regardless of the Investigator's assessment of causality for individual AE reports, the Sponsor will promptly evaluate all reported SAEs against

cumulative product experience to identify and expeditiously communicate possible new safety findings to Investigators and applicable regulatory authorities.

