
 • Change from baseline in the annualized utilization (IU/kg/year) of exogenous FVIII replacement therapy during Weeks 5-52 post-BMN 270 infusion, for subjects receiving FVIII prophylaxis during the 12 months prior to study entry, or change from baseline in the annualized utilization (mg/kg/year) of emicizumab during Week 27 to Week 52 post-BMN 270 infusion for subjects receiving prior emicizumab prophylaxis • Change from baseline in the annualized infusion rate (number/year) of exogenous FVIII replacement therapy during Weeks 5-52 post-BMN 270 infusion, for subjects receiving FVIII prophylaxis during the 12 months prior to study entry, or change from baseline in the annualized utilization (mg/kg/year) of emicizumab during Week 27 to Week 52 post-BMN 270 infusion for subjects receiving prior emicizumab prophylaxis • Change from baseline in the annualized number of bleeding episodes (number/year) requiring exogenous FVIII replacement treatment during Weeks 5-52 post-BMN 270 infusion for subjects receiving prior FVIII prophylaxis, or Weeks 27-52 post-BMN 270 infusion for subjects receiving prior emicizumab prophylaxis from baseline 		

Mean change from baseline and associated 95% confidence interval will be calculated for the total score of Haemo-QoL-A at Week 52 post-BMN 270 infusion as well.
		

The incidence of AEs will be summarized by system organ class, preferred term, relationship to study drug, seriousness, and severity. Clinical laboratory test values, vital signs, vector shedding and immune response parameters will be summarized descriptively by visit.
		

The final analysis for the study will be performed after all subjects have been followed for 52 weeks post-BMN 270 infusion (or have discontinued study participation prior to Week 52). No formal interim analysis is planned. Informal analyses (ie, no hypothesis testing) may be performed at different timepoints to assess efficacy and safety over time. The primary efficacy endpoint for such analyses involves hFVIII activity, as measured by chromogenic substrate assay, and is defined as median FVIII activity during a specific 4-week time interval post-BMN 270 infusion.
		

Details of the planned analyses will be specified in the SAP.
		

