8 STUDY OBJECTIVES

The primary efficacy objective of the study is to:

- Assess the efficacy of BMN 270 with prophylactic corticosteroids defined as FVIII activity, as measured by chromogenic substrate assay, during Weeks 49-52 following intravenous infusion of BMN 270

The secondary efficacy objectives of the study are to:

- Assess the impact of BMN 270 with prophylactic corticosteroids on the use of exogenous FVIII replacement therapy from Week 5 to Week 52 for subjects receiving prior FVIII prophylaxis or on use of emicizumab from Week 27 to Week 52 for subjects receiving prior emicizumab prophylaxis
- Assess the impact of BMN 270 with prophylactic corticosteroids on the number of bleeding episodes requiring exogenous FVIII replacement therapy from Week 5 to Week 52 for subjects receiving prior FVIII prophylaxis or on use of emicizumab from Week 27 to Week 52 for subjects receiving prior emicizumab prophylaxis
- Assess the impact of BMN 270 with prophylactic corticosteroids on quality of life as measured by the Haemo-QoL-A questionnaire at Week 52 of the study compared to baseline

The tertiary efficacy objective of the study is to:

- Assess the impact of BMN 270 with prophylactic corticosteroids on patient-reported outcomes (PROs) (other than Haemo-QoL-A) at Week 52 of the study compared to baseline

The exploratory efficacy objective of the study is to:

- Assess the efficacy of BMN 270 with prophylactic corticosteroids defined as FVIII activity, as measured by chromogenic substrate assay, during Weeks 49-52, following intravenous infusion of BMN 270 for subjects with detectable AAV5 total antibodies below the minimum required dilution at Screening

The safety objectives of the study are to:

- Evaluate the safety of BMN 270 with prophylactic corticosteroids during the first 52 weeks following intravenous infusion
- Assess the long-term safety of BMN 270 with prophylactic corticosteroids

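### The Grade 4/5 trigger for urgent DMC review counts only events related to BMN 270, although every subject also receives prophylactic corticosteroids, and the two trigger lists state no difference in enrolment while the DMC evaluates

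*Protocol*

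**What the plan says.** Section 9.3.3.1 reads the same in the original protocol (28 February 2020) and in Amendment 1 (15 September 2020). It has two lists, and every event on either one requires urgent DMC evaluation.

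- **First list, six items.** Item 2 is "The occurrence of Grade 4 or Grade 5 adverse events assessed as related to study drug". For all six, "further enrollment into the trial will be temporarily put on hold if recommended by the DMC", with a reference to Section 9.1.
- **Second list, two items.** "Further enrollment into the trial will continue while DMC evaluation is ongoing, unless deemed otherwise by the DMC".

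Section 4 (Definition of Terms) treats study drug and investigational product as the same thing, and Section 9.4.2.1 describes that product as BMN 270. Section 9.4.8.2 starts every subject on prophylactic corticosteroids on Day 1, and Section 9.1 gives the course as 19 weeks. The first safety objective in Section 8 is to "Evaluate the safety of BMN 270 with prophylactic corticosteroids during the first 52 weeks following intravenous infusion". Section 10.3.3.3 of the original protocol has the investigator assess the "relationship of an AE to the study drug and/or corticosteroids and/or other immunosuppressant agents". Item 6 of the Amendment 1 summary of changes adds an option to rate relatedness to other systemic immunosuppressive agents, and gives safety monitoring and risk:benefit assessment as the reason.

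**The concern.** The trial tests a combination, but the Grade 4/5 trigger looks at one component of it. Section 7.4 says that the effect of prophylactic corticosteroids still needs investigation and reports unwanted effects of high or prolonged corticosteroid exposure. Section 9.4.8.2 foresees preventive measures against ulcers, osteoporosis and infection. A fatal infection judged to be caused by the corticosteroid and not by BMN 270 is thus a foreseeable event, and it meets no item on either list.

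The second problem is the enrolment wording. The lists are built as an escalation, but the text does not say what the escalation changes while the DMC evaluates. BMN 270 is given once and cannot be withdrawn, so the interval between an event and the DMC's decision is when the enrolment status of later subjects matters.

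**Working it through.** **Check 1: exposure.** The plan's own figure is a 19-week course. Table 9.1.6 of the original protocol has 20 dose columns: nine at 40 mg (Day 1 and Weeks 1 to 8), two each at 35, 30, 25 and 20 mg, and one each at 15, 10 and 5 mg. That is 9 + 8 + 3 = 20 columns, or Day 1 plus 19 weeks, which agrees.

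**Check 2: which triggers depend on relatedness.**

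| List | Trigger | Relatedness condition? |
|---|---|---|
| First, 1 | Liver dysfunction by ALT criteria | No (only extra-hepatic ALT rises are excluded) |
| First, 2 | Grade 4 or 5 AE | **Yes: study drug** |
| First, 3 | "The occurrence of an AE of hepatic failure" | No |
| First, 4 | High-titer FVIII antibodies, two subjects | No |
| First, 5 | "The occurrence of any cancer (except non-melanoma skin cancer) at any point after BMN 270 infusion" | No |
| First, 6 | Thromboembolic event with FVIII above 150 IU/dL | No |
| Second, 1 | High-titer FVIII antibodies, one subject | No |
| Second, 2 | Thromboembolic event, one subject | No |

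The condition appears in 1 of 8 triggers. The events that fall through are Grade 4 or 5, rated related to corticosteroids or another immunosuppressant, rated not related to BMN 270, and not covered by the other seven rows.

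**Check 3: how often this could arise.** The documents give no rate, so the per-subject risk p is an assumption. With 20 subjects, the chance of at least one such event is 1 − (1 − p)^20:

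| Assumed p | Chance of at least one in 20 |
|---|---|
| 1% | 1 − 0.99^20 = 18% |
| 2% | 1 − 0.98^20 = 33% |
| 5% | 1 − 0.95^20 = 64% |
| 10% | 1 − 0.90^20 = 88% |

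This shows only that the question is not academic if the risk is a few percent. It is not an estimate for this trial.

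**Check 4: enrolment between the event and the DMC's decision.**

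- First list: a hold follows if the DMC recommends one. Section 9.1, to which the sentence refers, says only that the DMC may decide on a pause. Nothing is stated for the time before that.
- Second list: enrolment continues unless the DMC decides otherwise.

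Lists with a hold that takes effect before the DMC acts: 0 of 2. Yet the same type of event moves up from the second list to the first as it becomes more serious. Antibodies in one subject are on the second list and in two subjects on the first. A thromboembolic event is on the second list, and with FVIII activity above 150 IU/dL on the first. No stated consequence for enrolment follows from that move until the DMC has decided.

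**The case against.** The strongest reply is that nothing is hidden. In the original protocol, Grade 4 and 5 events are always reported as serious adverse events (Section 10.3.3.2), all such events reach the sponsor within 24 hours whether or not related to study drug (Section 10.5.1), and the sponsor evaluates them whatever causality the investigator assigns (Section 10.3.3.3). The DMC reviews safety continuously and may pause enrolment on any emerging data (Sections 9.1 and 15). The guidance table in Section 10.3.3.3 rates the product and corticosteroids jointly and calls an event related even when other causes could explain it, so many events in the first 19 weeks may be rated related to BMN 270 as well. All this stands and makes the gap small. It does not close it: Section 9.3.3.1 exists because the protocol wanted some events to go to the DMC urgently and not at routine review.

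Three stronger readings are tempting and not supported.

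- A reader might infer that the adverse event summary also counts only BMN 270-related events. It does not. "The incidence of AEs will be summarized by system organ class, preferred term, relationship to study drug, seriousness, and severity" means that all events are summarised and that relationship is one breakdown. A further breakdown by relationship to corticosteroids is ordinary SAP content.
- A reader might infer that urgent DMC review as a whole is tied to BMN 270. Seven of the eight triggers carry no relatedness condition.
- A reader might infer that the first list orders enrolment to continue. It is silent on the interval, and the Medical Monitor must approve each enrolment (Section 9.4.5). The defect is the silence.

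The cumulative dose on the example schedule, 8 × 7 × 40 + 7 × 250 = 3,990 mg, describes exposure. It does not measure missed events.

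**Conclusion.** Two narrow points stand on the text of Section 9.3.3.1. Item 2 leaves out Grade 4/5 events attributed only to corticosteroids or other immunosuppressants, although the safety objective is the combination and relatedness to those agents is assessed. And the two lists state no difference in enrolment before the DMC acts, although they are built as an escalation.

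The size is 1 trigger of 8, with no event rate derivable from the documents. Neither point affects the primary analysis or removes these events from safety reporting. This is a cheap improvement to safety oversight.

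The conclusion assumes that study drug in item 2 carries its defined meaning and that the DMC Charter, which was not available here, does not already widen the trigger or set the interim enrolment status. The Amendment 1 text at hand stops at Section 10.2.1, so the causality wording is taken from the original Section 10.3.3.3 and from the Amendment 1 summary. The amended Sections 10.3.3.3 and 14.7 could not be read.

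**What to change.** 1. In Section 9.3.3.1, first list, reconcile item 2 with the safety objective and the causality categories already assessed, so that Grade 4/5 events rated related to corticosteroids or other immunosuppressive agents also go to urgent DMC evaluation.
2. Reconcile the two enrolment sentences. The first list should state what enrolment does between the event and the DMC's recommendation, so that the difference from the second list is explicit. Which events warrant a hold is for the sponsor and the DMC to decide.
3. Carry the same wording into the DMC Charter.

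As a suggestion only, the SAP could add adverse event incidence by relationship to corticosteroids and to other immunosuppressants.

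The cost is a few words in a protocol amendment and possibly an extra ad hoc DMC review. Item 2 needs no new data, because the causality assessment is already made.
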